This approval is issued under Colorado State University's Federal Wide Assurance 00000647 with the Office for Human Research Protections (OHRP). If you have any questions regarding your obligations under CSU's Assurance, please do not hesitate to contact us.

Please direct any questions about the IRB's actions on this project to:

IRB Office - [contact]; [contact]
[name], Senior IRB Coordinator - [contact]; [contact]
[name], IRB Biomedical Coordinator - [contact]; [contact]

[name]

Continuing renewal has been reviewed at the convened meeting on March 22, 2018. Continuation has been approved to recruit the remaining participants with the approved recruitment and consent procedures. This renewal acknowledges an

Research Integrity & Compliance Review Office
Office of the Vice President for Research
[name] eprotocol
[contact]
[contact]

error in the initial approval letter generated by the IRB in that it should have stated approval for recruitment of 60 participants. This renewal includes two deviation reports that were assessed and two proposed amendments in response to the reports. These amendments include expanding enrollment to include participants with 10-day course of antibiotics with medical monitor support and increased enrollment a total of 200 participants. This number is to ensure participants completing the study will amount to 60 individuals. This is in response to large number of screen fails and withdrawals. Approved documents include: Consent, version dated 01March2018.

Approval Period: March 22, 2018 through March 21, 2019
Review Type: FULLBOARD
IRB Number: 00010468
Funding: AstraZeneca

Continuing review.....	1
Personnel Information.....	3
Subject Population.....	6
Study Location.....	7
General Checklist.....	7
Funding.....	9
Expedited Paragraphs.....	10
Purpose, Study Procedures, Background.....	12
Radioisotopes or Radiation Machines.....	19
Medical Equipment for Human Subjects and Laboratory Animals; Investigational Devices.....	20
Drugs, Reagents, or Chemicals.....	20
Subject Population (a-g).....	21
Subject Population (h-m).....	24
Risks.....	27
Benefits, Procedures to Maintain Confidentiality.....	32
Potential Conflict of Interest.....	33
Informed Consent.....	34
Assent Background.....	35
HIPAA.....	35
Attachments.....	37
Obligations.....	42

Event History.....	43
--------------------	----

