We originally requested 60 overweight/obese adult volunteers (men and women) will be enrolled. Additionally it was stated in the protocol- "However, the number enrolled maybe higher in the event of enrollment of replacement subjects for dropout(s) that discontinued for reasons other than an adverse event due to study medication. In the event of a replacement subject being enrolled, this subject will complete all visits".
Please also note- the approval letter states approval for 50. To clarify the above statement, as a part of this continuing review we are amending the protocol to request recruitment of a total of

Protocol Title: Does Dapagliflozin Provide Additional Health Benefits To Dietary Counseling For Weight Loss?
Clinical Research Protocol Title: Dapagliflozin Promotes Favorable Health Benefits That Are Independent Of Weight Loss In Overweight/Obese Adults

Protocol Type: Biomedical

Date Submitted: 03/01/2018

Approval Period: Draft

Important Note: This Print View may not reflect all comments and contingencies for approval. Please check the comments section of the online protocol.
Questions that appear to not have been answered may not have been required for this submission.
Please see the system application for more details.

200 individuals.

2. a. Reasons and number of withdrawals from the research (both subject and investigator initiated) since the last approval date.

Declined participation: 13
Non-compliance: 2
Screened out: 9
Moved to 14-5529H: 3

b. Number of subjects lost to follow-up since the beginning of the study.

14

c. Please summarize any protocol deviations/violations or unanticipated problems (UPs)/adverse events (AEs) since the last continuing review or original approval (if this is your first continuing review). Please indicate if any of the unanticipated problems/events are being reported to the IRB for the first time. If you have or will make changes to your protocol as a result of any unanticipated problem/event or adverse event, please summarize those changes in Question #5 below.

Please see adverse event log in the attachments.
Please see deviations: Course of antibiotics was report verbally to IRB on 1/31/2018. Wrong pill bottle 1st, Extended Invention Period, and Duration of invention are first time reports.

e. Complaints about the research during the last year.

none

3. A summary of any recent findings, literature, or other relevant information (especially pertaining to risks), if applicable.

none

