2. Weight loss associated with dietary counseling and the use of Dapagliflozin (SGLT2 inhibition) is characterized by normal circulating satiety signals rather than the usual diet-induced changes in circulating peptides that increase hunger and reduce satiety.

c) Proposed Start Date (may not precede IRB approval date):

On receipt of IRB approval.

2.

Study Procedures (If this is a student project, the methods section of the thesis or dissertation proposal must be attached in section #16 - Attachment section.)

a) In lay language, describe all the procedures, from screening through end-of-study, that the human subject must undergo in the research project, including study visits, drug treatments, randomization and the procedures that are part of standard of care. Please note: Do NOT respond "See Attachment Section." If you would like to add tables, charts, etc., attach those files in the Attachment section (#16).

OVERVIEW

This is a randomized, prospective, placebo-controlled, double blind, repeated measures study. 60 overweight/obese adults (body mass index > 27.5 kg/m²) will be recruited for participation and randomly assigned to one of two 12 week treatments: (1) daily oral administration of Dapagliflozin with dietary counseling to promote weight loss; or, (2) daily oral administration of a placebo with dietary counseling to promote weight loss.

Study participants will report to the research facilities on the Colorado State University main campus on 29 separate occasions:

Visit 1: study participants will undergo screening: medical history, 12-lead electrocardiogram and blood pressure assessment at rest and during incremental exercise to volitional exhaustion, blood sampling, and measurement of body composition.

Visit 2: an oral glucose tolerance test will be performed and resting metabolic rate and blood pressure will

Protocol Title: Does Dapagliflozin Provide Additional Health Benefits To Dietary Counseling For Weight Loss?
Clinical Research Protocol Title: Dapagliflozin Promotes Favorable Health Benefits That Are Independent Of Weight Loss In Overweight/Obese Adults

Protocol Type: Biomedical

Date Submitted: 03/01/2018

Approval Period: Draft

Important Note: This Print View may not reflect all comments and contingencies for approval. Please check the comments section of the online protocol.
Questions that appear to not have been answered may not have been required for this submission.
Please see the system application for more details.

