***** Subject Population (a-g) *****

Protocol Title: Does Dapagliflozin Provide Additional Health Benefits To Dietary Counseling For Weight Loss?
Clinical Research Protocol Title: Dapagliflozin Promotes Favorable Health Benefits That Are Independent Of Weight Loss In Overweight/Obese Adults

Protocol Type: Biomedical

Date Submitted: 03/01/2018

Approval Period: Draft

Important Note: This Print View may not reflect all comments and contingencies for approval. Please check the comments section of the online protocol.
Questions that appear to not have been answered may not have been required for this submission.
Please see the system application for more details.

8.

Subject Population - In the space below, please detail the participants that you are requesting to recruit (include requested participant number and description of each group requested). (Input N/A if not applicable)

a) Requested Participant Description (Include number of participants that you plan to study and description of each group requested, if applicable).

60 overweight/obese adult volunteers (men and women) will be studied. However, the number enrolled may be higher in the event of enrollment of replacement subjects for dropout(s) that discontinued for reasons other than an adverse event due to study medication. In the event of a replacement subject being enrolled, this subject will complete all visits. Therefore we would like to enroll 200 participants.

Participants previously enrolled in 14-5531H and withdrawn due to new information will be contacted per for future enrollment in this study. Several procedures, such as screening and DEXA, OGTT, will not be redone, but will be released for the purposes of this purpose. You can find the participant letter that went out to those participants in the attachments section.

b) What is the rationale for studying the requested group(s) of participants?

Adults who are overweight/obese are at the greatest risk of developing type 2 diabetes, thus overweight/obese adults potentially have the most to gain should the outcome of the study prove favorable. Inclusion of adults already diagnosed with diabetes might complicate the interpretation of the data; that is, as a consequence of the patho-physiology associated with diabetes, the response to our feeding treatment with or without Dapagliflozin may differ in adults with diabetes compared with adults who are diabetes free.

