Baseline (pre-counselling) differences between placebo and SGLT2 inhibition groups were compared using independent Student t-Tests. Consistent with the experimental design (randomized, double-blind, parallel, repeated measures) the influence of SGLT2 inhibition on the physiological responses to dietary counselling was examined using two-way (group: placebo vs. SGLT2 inhibition x time: before vs. after dietary counselling) analysis of variance (ANOVA). The influence of SGLT2 inhibition and dietary counselling on the dynamic responses to oral glucose ingestion were examined using three-way ANOVA (placebo vs. SGLT2 inhibition x before vs. after dietary counselling x time points during the OGTT). Pairwise multiple comparison procedures were performed using the Holm-Sidak Method. Relations of interest were described using Pearson product-moment correlations. The level of statistical significance was set at $P<0.05$. Data are reported as mean and standard deviation, unless otherwise indicated. Calculations were performed using commercially available statistical software (SigmaStat 3.0, Systat Software Inc., San Jose, California, USA).

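### The before/after ANOVA does not adjust for baseline, drops people without a final value and leaves the serial weights unused; a baseline-adjusted analysis would do better at little cost

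*Combined protocol and SAP*

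**What the plan says.** The Statistical Analysis Plan is one paragraph. The drug effect "was examined using two-way (group: placebo vs. SGLT2 inhibition x time: before vs. after dietary counselling) analysis of variance (ANOVA"). The glucose-tolerance curves "were examined using three-way ANOVA (placebo vs. SGLT2 inhibition x before vs. after dietary counselling x time points during the OGTT"), which keeps the same two-level before/after factor. The SAP calls the design repeated measures but states no subject term for the ANOVA. It names no primary outcome, analysis set or missing-data method, and gives the weigh-ins no role.

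Protocol section 2a (Visits 4-27) schedules weighing twice a week for six weeks, then once or twice a week for six more, depending on whether the participant is meeting the weight goal. The glucose tolerance test, resting metabolic rate and blood pressure are repeated once, at Visit 28. Appetite and body composition are repeated once, at or just after Visit 29. No separate body weight is listed for Visits 28-29, and the SAP does not say which weight counts as the after value.

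On numbers, the IRB approval letter raises enrolment to 200 and explains: "This number is to ensure participants completing the study will amount to 60 individuals". It adds: "This is in response to large number of screen fails and withdrawals". The section 2a overview says 60 adults "will be recruited for participation and randomly assigned to one of two 12 week treatments". Section 8a says 60 will be studied and allows "enrollment of replacement subjects for dropout(s) that discontinued for reasons other than an adverse event due to study medication".

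Continuing review item 2a, headed "Reasons and number of withdrawals from the research (both subject and investigator initiated) since the last approval date", lists 13 who declined, 2 non-compliant, 9 screened out and 3 moved to another protocol. Item 2b gives 14 lost to follow-up. Item 2c reports deviations: "Wrong pill bottle 1st, Extended Invention Period, and Duration of invention are first time reports". Two sponsor protocols are listed under Attachments and were not available; they may settle some of these points.

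**The concern.** A group-by-time test with two time levels uses less of the data than the trial collects. If the before/after correlation is well below 1, analysing change is less precise than adjusting for baseline. Anyone who leaves before Visit 28 or 29 adds nothing to the test, even with many on-treatment weights on file. If the reasons for leaving differ between arms and relate to response, comparing those who stay is no longer protected by randomisation. The SAP states no method for this, although the IRB letter cites withdrawals as a reason for raising enrolment.

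**Working it through.** The documents contain no power or sample-size calculation, so there is no figure of the plan's own to reproduce. One-to-one allocation is assumed throughout, because the protocol gives no ratio; 60 completers then means 30 per arm.

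**1. What the ANOVA tests.** In a 2x2 repeated-measures model (subject, time, group x time), the interaction is the difference between arms in mean change.
- 60 simulated subjects with complete data: the model and a t-test on change both give t = -0.956 on 58 df.
- 11 of the 60 left with a baseline only: the model fitted to all 60 gives estimate -0.340, t = -0.427, 47 df. The 49 completers alone give exactly the same.

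So people without a final value contribute nothing. Fitting the ANOVA without a subject term would be no remedy: the interaction's standard error grows by 1/sqrt(1 - r), which is 1.4 at r = 0.5 and 2.2 at r = 0.8.

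**2. Unused weights.** 6 x 2 = 12 in weeks 1-6, plus 6 x (1 to 2) = 6 to 12 in weeks 7-12, gives 18 to 24. At most one can enter as the after value.

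**3. Precision lost by not adjusting for baseline.** With equal variances and before/after correlation r (assumed), the variance is proportional to 2(1 - r) for change and to 1 - r^2 with baseline adjustment. The ratio is (1 + r)/2.
- r = 0.5: ratio 0.75; 30/0.75 = 40 per arm.
- r = 0.7: ratio 0.85; 30/0.85 = 35 per arm.

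**4. What the dropout counts allow.** The continuing review counts 80 studied. Three readings:
- Decliners never started and all 14 lost overlap other categories: 2/(80 - 9 - 3 - 13) = 2/55 = 4%.
- Decliners never started, no overlap: 16/55 = 29%.
- All 13 decliners and all 14 lost are separate dropouts: 29/(80 - 9 - 3) = 29/68 = 43%.

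These are interim counts with recruitment still open and no split by arm. They serve only as scenarios and do not bound the final dropout rate.

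**5. Illustration of bias for body weight.** Assumptions: no drug effect; equal dropout rates; week-6 loss mean 2.0 kg (SD 2); week-12 loss mean 4.0 kg (SD 3.5); correlation 0.85; dropout log-odds rise by 0.5 per kg less lost at week 6. The standard error is 3.5 x sqrt(2/30) = 0.90 kg. Each cell gives bias and two-sided false-positive rate.

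| Dropout | Same pattern in both arms | Half as strong in one arm | One arm only |
|---|---|---|---|
| 4% | 0 kg, 5% | 0.05 kg, 5.0% | 0.1 kg, 5.2% |
| 29% | 0 kg, 5% | 0.33 kg, 6.6% | 0.7 kg, 13% |
| 43% | 0 kg, 5% | 0.45 kg, 8.0% | 1.1 kg, 22% |

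Using the mid-study weight brings the simulated bias to about 0. In a separate simulation with a true effect of -1.00 kg, 40 per arm, completion of 88% to 63% and the same mechanism in both arms, the completer estimate was -0.90 to -0.83 kg. Using serial weights it was -0.98 to -1.00 kg.

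**6. Precision gained from the weigh-ins.** Variance per arm is SD^2 x [(1 - r^2)/30 + r^2/n], where n counts everyone with a mid-study weight and r is its correlation with the final weight change. At 43% dropout n = 30/(1 - 0.426) = 52.3. With r = 0.85: 0.2775/30 + 0.7225/52.3 = 0.0231, an effective n of about 43 per arm. That is the ceiling. If half the dropouts have a mid-study weight, it is about 37.

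**7. Outcomes measured once after treatment.** Take the one-arm-only case at 43%, with outcome change correlated 0.4 with week-12 weight loss and before/after correlation 0.6 (both assumed). Approximate bias: (1.058/3.5) x 0.4 x sqrt(2 x 0.4) = 0.108 SD. Two simulations gave 0.095 and 0.109 SD for the change analysis. A model holding only the outcome's own baseline gave 0.096 and 0.109 SD, so it corrects nothing here. Adding the weigh-ins as auxiliary data reduced the second figure to 0.001 SD.

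**The case against.** The stated aims are health benefits beyond weight loss and satiety signals. No primary outcome is named, and the weigh-ins serve mainly to run the counselling. Apart from weight, every outcome has a single post-treatment assessment, for which a before/after factor fits the data collected. In a randomised trial the change-score test is valid; baseline adjustment is better, not the only defensible choice. All of this stands, and it limits the longitudinal part of the point to weight and to an auxiliary role elsewhere.

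A reader might infer that dropout has biased this trial, or that its false-positive rate is 13% to 22%. The documents do not support that. Those rates come from an extreme case in a double-blind trial, under assumed parameters. The adverse-reaction frequencies in section 9b are not discontinuation rates and come with no placebo comparison. The replacement wording in section 8a foresees drug-related dropout but does not show it.

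A reader might also infer that completers are the declared analysis set. They are not: a recruitment target in an IRB letter does not define one. The wrong-bottle report does not show that anyone received the other arm's treatment, since its details were not available.

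**Conclusion.** The point holds as a choice of a weaker method where a better one is cheap. Under the repeated-measures reading, the planned test is a comparison of change among people with both values, unadjusted for baseline, with 18 to 24 weights per participant unused. The firm part of the cost is precision: 30 per arm could act as about 35 to 40 with baseline adjustment, at an assumed correlation of 0.7 to 0.5. For weight, the weigh-ins could raise the effective number to about 43 at most, and only with heavy dropout and a mid-study weight on every dropout.

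Bias is a possibility, not a finding. It is negligible at about 4% dropout, and absent if the dropout pattern is the same in both arms and the drug has no effect. Its size and direction in this trial cannot be computed. Deviation handling and the meaning of 60 are minor reporting points.

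**What to change.** 1. For outcomes with one post-treatment assessment (glucose-tolerance summaries, blood pressure, resting metabolic rate, appetite, body composition), replace the group-by-time test with ANCOVA or a baseline-constrained model, in all randomised participants by assigned arm. ANCOVA alone cannot use a person with no final value, so state the missing-data method. If dropout is not negligible, bring in the weigh-ins as auxiliary variables through multiple imputation or a joint model.
2. Analyse body weight with a likelihood-based mixed model on baseline plus one weight per week, because weigh-in frequency in weeks 7-12 depends on weight loss. State which weight is the end-of-treatment value.
3. Keep the completer ANOVA as a sensitivity analysis. Report randomised, discontinued (with reason) and completed participants by arm.
4. State how the reported deviations are handled. Reconcile the IRB letter, the section 2a overview and section 8a on whether 60 means randomised, studied or completed, and on who is replaced.

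The cost is SAP wording, a clarifying sentence in section 8a, mixed-model or imputation software and slightly more analysis work. No extra patients or visits are needed. The SAP is written in the past tense and the Event History shows the protocol as expired, so the change would now be a reanalysis and should be labelled as one.

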Blood sampling – Blood (~ 20 ml) will be sampled from an antecubital or hand vein for subsequent analysis of circulating factors pertinent to inclusion/exclusion criteria, including glucose, aspartate aminotransferase, alanine aminotransferase, and total bilirubin. These blood analyses will be performed in on-site (Piccolo Xpress, Abaxis, Union City, CA). Testing for Hepatitis B/C will be performed at a local, external clinical lab (e.g. University of Colorado-Health North). Per the Medical Monitor's discretion follow up blood draws maybe requested.

Visit 2: Resting Metabolic Rate (ventilated hood technique, indirect calorimetry) for 45 minutes and blood pressure will be measured. An oral glucose tolerance test will be performed.

Protocol Title:	Does Dapagliflozin Provide Additional Health Benefits To Dietary Counseling For Weight Loss? Clinical Research Protocol Title: Dapagliflozin Promotes Favorable Health Benefits That Are Independent Of Weight Loss In Overweight/Obese Adults
Protocol Type:	Biomedical
Date Submitted:	03/01/2018
Approval Period:	Draft
Important Note:	This Print View may not reflect all comments and contingencies for approval. Please check the comments section of the online protocol. Questions that appear to not have been answered may not have been required for this submission. Please see the system application for more details.

These procedures are standard for our lab. Each of the procedures is currently active in other IRB-approved protocols (e.g. 14-5201H).

Blood pressure will be determined three times using the left arm via standard procedures. Each assessment will be separated by 3 minutes. The mean of the three measurements will be recorded.

Participants will report to the laboratory early in the morning, following a 12-hour fast and 24-hour abstention from exercise. An intravenous catheter will be inserted into an antecubital or hand vein and kept patent with a saline drip. Following baseline blood sampling for fasting glucose and insulin, participants will ingest 75 g of dextrose dissolved in 250 ml of water over 10-minutes. Venous blood (~ 9 ml) will be sampled at time 0 (baseline) and 5, 10, 15, 20, 30, 45, 60, 75, 90 105 and 120 minutes for determination of concentration of blood glucose (2300 STAT Plus Glucose Lactate Analyzer, YSI Inc., Yellow Springs, Ohio), and insulin (commercially available assay).

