Prior to the start of the oral glucose tolerance test, venous blood (~ 20 ml) will be sampled, and plasma/serum and red cells isolated and stored at -70°C for subsequent analysis of circulating markers of inflammation (High sensitive C-Reactive Protein, Tumor Necrosis Factor Alpha, and Interleukin 6) and oxidative stress (oxidized low density lipoprotein concentration, and thiobarbituric acid reactive substances).

Visit 3: Appetite and hunger will be assessed.

These procedures are standard for our lab. Each of the procedures is currently active in other IRB-approved protocols (e.g. 12-3567H).

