Please see the system application for more details.

Visits 4-27: During the first 6 weeks participants will meet with a study counselor 2 times per week for dietary counseling and measurement of body weight. During the second 6-week period they will meet 1-2 times per week for dietary counseling and body weight measurement, depending on whether or not they are meeting weight loss goals. If they are losing weight as prescribed, they will meet only once per week, but if they are not meeting weight loss goals they will meet 2 times per week. Participants will need to fast for 10 hours prior to the weigh-in. On 2 random counseling occasions between weeks 4 and 10, they will be asked to recall what they ate during the previous 24 hours. If participants fail to achieve their target body weight (within 1 kg or 2.2 lbs) on three consecutive weighing sessions, they will be provided with additional counseling and instructions to aid in achieving your target body weight.

During the first two weeks of the 12 week intervention, participants will ingest one pill daily (5 mg DAPA) and for the remaining 10 weeks participants will ingest 2 pills daily (a total of 10 mg DAPA). On 3 random weigh-in occasions between weeks 4 and 10, participants will be asked to recall what they ate during the previous 24 hours.

Visit 28: Resting Metabolic Rate Test, Oral Glucose Tolerance Test, and Blood Pressure will be measured (e.g. the final week of daily ingestion of Dapagliflozin). See description of Visit 2.

Visit 29: in the HPCRL appetite and hunger will be assessed this visit will occur in week 12 (e.g. during the final week of daily ingestion of Dapagliflozin). Body composition will be measured at this visit or early the following week (e.g. week 13). The study participants will also be given the 3-day food intake record form to be completed and returned to the research team.

b) Explain why human subjects must be used for this project.

Dapagliflozin is approved for human use. Due to potential species differences it would not be appropriate to perform these studies on experimental animals.

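### Where an outcome has one pre and one post value, ANCOVA on the baseline already collected would usually be more precise than the planned group × time ANOVA, and it removes chance baseline imbalance

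*Combined protocol and SAP*

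**What the plan says.** The Statistical Analysis Plan is one paragraph. It examines the physiological responses to counselling by "two-way (group: placebo vs. SGLT2 inhibition x time: before vs. after dietary counselling) analysis of variance (ANOVA", in a design it describes as randomised, parallel and repeated measures. It does not say which F test is the treatment test or what the error term is. No baseline covariate appears. Baseline is handled separately: "Baseline (pre-counselling) differences between placebo and SGLT2 inhibition groups were compared using independent Student t-Tests". Nothing is said about what follows if one of those tests is significant. The plan adds "Pairwise multiple comparison procedures were performed using the Holm-Sidak Method". Significance is set at 0.05, with sidedness not stated.

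The Study Procedures section shows that the covariate exists. At visit 2, "Resting Metabolic Rate (ventilated hood technique, indirect calorimetry) for 45 minutes and blood pressure will be measured"; for blood pressure, "The mean of the three measurements will be recorded". Before the glucose load at visit 2, blood is drawn for "circulating markers of inflammation (High sensitive C-Reactive Protein, Tumor Necrosis Factor Alpha, and Interleukin 6) and oxidative stress". After treatment, "Visit 28: Resting Metabolic Rate Test, Oral Glucose Tolerance Test, and Blood Pressure will be measured", with a reference back to the visit 2 description. Section 4 (Radioisotopes or Radiation Machines) gives one DEXA before treatment and one after.

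Visit 1 also includes "blood pressure assessment at rest and during incremental exercise to volitional exhaustion". Visit 2 is taken here as the blood pressure baseline because visit 28 repeats its procedure.

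**The concern.** With two time points, the within-subject group × time interaction is exactly the two-sample t-test on change (F = t²). It subtracts the whole baseline value, which is a baseline slope of 1. When the true slope is below 1, this has two consequences.

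- **Precision.** Part of the baseline noise is added back into the comparison. The trial aims for 60 completers, and the documents contain no power calculation, so there is no stated margin to give away.
- **Chance imbalance.** A baseline difference between arms leaks into the estimated effect with the opposite sign. The plan tests for such differences but commits to no response, so the handling could be decided after they are seen.

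The point covers every outcome with a single pre and a single post value: resting metabolic rate, blood pressure, the inflammation and oxidative-stress markers, and DEXA body composition. By the same logic it covers ad libitum buffet intake at visits 3 and 29. The OGTT curves and the hunger and hormone curves are outside it.

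**Working it through.** The documents give no effect size, SD, correlation or power, so there is no planned figure to reproduce.

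**Inputs from the documents**
- 60 completers (IRB approval letter).
- Two arms (Study Procedures, Overview).
- Significance level 0.05 (Statistical Analysis Plan).

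**Assumptions**
- 30 per arm and a two-sided test.
- Pre–post correlation ρ from 0.3 to 0.95.
- k = SD(post)/SD(pre), equal to 1 unless stated. The pre SD is 1.

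**Precision**

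- Change score, per-subject variance: 1 + k² − 2ρk.
- ANCOVA, residual variance: k²(1 − ρ²).
- The first minus the second is (1 − ρk)². It is never negative and is zero only at ρk = 1.
- ANCOVA pays for its extra parameter by a factor 1 + 1/(N − 4) = 57/56 at N = 60.
- With k = 1 the variance ratio, ANCOVA to change, is (1 + ρ)/2 × 57/56. At ρ = 0.5 this is 0.75 × 1.018 = 0.763, a loss of 24%.
- The ratio passes 1 at ρ = 2 × 56/57 − 1 = 0.965. Above that there is no gain.

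With unequal variances at ρ = 0.5:
- k = 0.8: 0.48/0.84 × 57/56 = 0.582, a loss of 42%.
- k = 1.2: 1.08/1.24 × 57/56 = 0.887, a loss of 11%.

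Detectable differences use the noncentral t with 58 df (change) and 57 df (ANCOVA), with the extra parameter included.

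| ρ | 0.3 | 0.5 | 0.7 | 0.8 | 0.95 |
|---|---|---|---|---|---|
| Information lost, k = 1 | 34% | 24% | 13% | 8% | 0.8% |
| Information lost, k = 0.8 | 49% | 42% | 36% | 35% | 47% |
| Information lost, k = 1.2 | 22% | 11% | 2% | −1.5% | 11% |
| Detectable at 80% power, planned (SD) | 0.87 | 0.74 | 0.57 | 0.465 | 0.23 |
| Detectable at 80% power, ANCOVA (SD) | 0.71 | 0.64 | 0.53 | 0.445 | 0.23 |
| Power of the interaction where ANCOVA has 80% | 62% | 69% | 74% | 77% | 80% |

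**Chance imbalance** (k = 1)

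The change estimate moves by −(1 − ρ) for each unit of baseline difference; the ANCOVA estimate moves by about 0. Baseline p < 0.05 occurs in 5% of randomisations per outcome, with a mean gap of 0.59 SD. At ρ = 0.5 that gap shifts the change estimate by 0.5 × 0.59 = 0.295 SD. The standard error is √(2 × 0.5) × √(2/30) = 0.258 SD.

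False-positive rates from null simulation, 3,000,000 trials per ρ:

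| ρ | 0.3 | 0.5 | 0.7 | 0.8 | 0.95 |
|---|---|---|---|---|---|
| Planned test, baseline p < 0.05 | 23.6% | 18.1% | 12.5% | 10.1% | 6.2% |
| Planned test, all other randomisations | 4.0% | 4.3% | 4.6% | 4.7% | 4.9% |
| Chance of both events | 1.2% | 0.9% | 0.6% | 0.5% | 0.3% |

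The two strata average to 5%: at ρ = 0.5, 0.05 × 18.1% + 0.95 × 4.3% = 5.0%. ANCOVA is at 5.0% in both strata. At ρ = 0.5 the 18.1% becomes 28.4% with k = 0.8 and 11.6% with k = 1.2.

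**If the SAP means a different test**

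At ρ = 0.5, for the difference that ANCOVA detects with 80% power, the group main effect has 29% power. A factorial ANOVA without a subject term has 38%, with type I error below 1%. The choice of F test therefore matters, and the plan does not state it.

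**The case against.** This is a preference between two valid analyses. Nothing in the plan is biased or contradictory, and the planned test keeps its 5% level. That stands, and it is why this is a suggested improvement and not an error.

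The size of the gain rests on a correlation the documents do not give, and that stands too. Averaging three blood pressure readings and recording metabolic rate over 45 minutes favours a high correlation, hence a small gain. At 0.95 with equal variances there is practically none, and with a 20% larger post SD at 0.8 ANCOVA is slightly worse. In the other direction, participants brought over from 14-5531H do not repeat procedures such as DEXA and OGTT (Subject Population, item 8a). Their baselines are older by an unstated interval, which favours a lower correlation. Resting metabolic rate, blood pressure and the markers share visit 2 with the OGTT and may be affected too. The number of such participants is not given.

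The high conditional error rates belong to 5% of randomisations per outcome, and the joint chance is at most 1.2% with equal variances. They describe what happens after an imbalance is seen; they do not show overall inflation.

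ANCOVA on follow-up gives no time effect or within-arm change, which the factorial ANOVA does. This is correct, but the within-arm Holm-Sidak comparisons can be kept beside it. They were not assessed here.

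Finally, the plan is in the past tense and the Event History shows the protocol expired in March 2019, so the analysis may already be done. Swapping models then would be a post hoc choice. This limits the form of the fix, not the statistical point.

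**Conclusion.** The point holds as an efficiency improvement on a valid test. With 30 per arm and equal variances, ANCOVA recovers from nothing to about a third of the information. The upper figure assumes a correlation of at least 0.3; at zero the formula gives 1 − 0.5 × 57/56 = 49%. The gain is material at correlations of 0.3 to 0.7 and negligible where ρ × SD(post)/SD(pre) is near 1. ANCOVA also settles chance baseline imbalance in advance.

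This rests on equal allocation, on the interaction with time within subject being the intended treatment test, and on an assumed correlation. The direction of the precision result is secure apart from a loss of at most about 2% (a factor of 57/56) near ρk = 1. Its size for any particular outcome is unknown.

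**What to change.** For each outcome with one pre and one post value, make the treatment test an ANCOVA: follow-up value on arm plus that outcome's own baseline (visit 2 for blood pressure). Report the adjusted arm difference with its 95% CI. This also names the treatment test, which the plan leaves open.

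Describe baseline by arm without significance tests, since adjustment no longer depends on them. Keep the three-way ANOVA for the OGTT curves. Within-arm comparisons may stay as description. State how many participants carry baselines over from 14-5531H and for which measurements.

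The cost is one degree of freedom and a few lines of SAP text, with no new data. If results are already known, leave the planned ANOVA in place and report the ANCOVA beside it, labelled as a reanalysis.
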